### Severity of symptoms

The rationale for choosing the severity in the first 2-4 days after seeing the doctor, is that this is the time when symptoms are the most severe, (9) the inflammation is at its worst and when antibiotics

might make a difference. The duration of minor symptoms on its own is of less concern to children and carers and the time for resolution of all symptoms will be documented.

#### Side effects

Diarrhoea, rash, or nausea are common side effects of treatment and will also be recorded in the daily diary. (10)

#### Quality of life

Preference based measurement of quality of life in young children is under-developed, especially for children under 5 years. Current validated instruments in young children such as CH9D and EQ-5D are for children aged above 7, while HUI 2 and HUI 3 are intended for children age 5 years and older. EQ-5D-Y version can be used for children 7 years old and parent proxy for age 4-7. No single validated preference based measurement of quality of life exists in the current literature which can be applied in our study population (age 6 months to <12 year old). After discussion, we have decided to use EQ-5D-Y version. The questionnaire will be completed by parents/carers proxy for all patients at days 0,1,7,14,21 and 28). For children younger than age 4, only EQ5D VAS will be used.

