## 1.8. Measurement of costs/outcomes

Primary outcome: duration of moderately bad symptoms (from validated symptom diary). Secondary outcomes: symptom severity (days 2-4); duration of symptoms until very little problem; the development of new or worsening symptoms; complications. Health related quality of life will be measured by proxy methods in which The EuroQoL (EQ5DY) will be completed by patients or carers for age older than 7, children will complete the questionnaire separately too on days 0,1,3, 7, 14 21 and 28. Follow-up (at 1 month): measure lung function (if aged 6+).

Outcome parameters for observational study: development of new or worsening symptoms; complications, diagnosis of pneumonia based on chest X-ray.

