### 5.14. Cost-effectiveness

The economic analyses will be taken from the NHS and PSS perspective. All resource usage will be priced based on published information (BNF, National reference costs and PSSRU). Accumulated costs and QALYs will be calculated through area under the curve methods for each patients. Missing value will be imputed using multiple imputation approach. Generalised linear model will be used to estimates the differences in costs and QALYs between the study groups and adjusted baseline

difference. If the intervention is proved to be effective, incremental costs per symptomatic day prevented and cost per quality adjusted life year gained will be estimated. Cost effectiveness acceptability curves will also be produced to illustrate the uncertainty.

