## 8. HEALTH ECONOMICS

The primary economic analysis will be taken from a societal perspective but will also include the NHS and Personal Social Services (PSS) perspective. For NHS and PSS costs, we will collect data on medication, primary care visits, hospital stays, outpatient appointments and A&E attendances. All the information including adverse events will be collected through notes review forms at the end of the trial 28 days and CRFs. For the societal perspective, we will collect out-of-pocket spending, and time off work for parents taking care of children through a short questionnaire at the end of the study. All itemised resource usage will be weighted by their corresponding unit costs based on published sources (BNF, PSSRU and NHS reference costs).

We will measure the quality of life based on parents/cares proxy from EQ5DY, and the Visual analogue scale (VAS) used as part of the EQ5DY. The EQ5DY will be included as well as PedsQL™ (Pediatric Quality of Life Inventory™) on the basis that it measures quality of life at a point in time, and will be used in conjunction with the clinical outcome measures at days (1,7,14,21,28). This is important for an acute condition, and EQ5D was very helpfully used in the GRACE studies in adults to document change over time (and did change significantly which suggests it is likely to be useful in this population too). We will take this opportunity to investigate the associations between the different methods, which will help inform the use of proxy methods to measure children's' quality of life.

We will conduct an economic evaluation alongside the clinical trial. Accumulated costs and QALYs for each individual will be calculated based on an "area under the curve" approach. The cost-effectiveness analysis will be measured as costs per symptomatic day prevented and the incremental cost per quality adjusted life year gained (QALY). Generalized linear models will be employed to investigate the cost difference between interventions adjusted for baseline characteristics and bootstrapping methods will be used to produce incremental cost-effectiveness ratios and confidence ellipses. Cost-effectiveness acceptability curves will also be produced to reflect the probability of the intervention will be cost-effective at different given willingness to pay value per QALY gained. The cost effectiveness of antibiotics will be estimated in each subgroup.

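### Three different EQ-5D-Y schedules are given, and two have no measurement between day 1 and day 7, so the area-under-the-curve QALY can understate an effect concentrated on days 2 to 4

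*Protocol*

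**What the plan says.** The days for the EQ-5D-Y appear in three places in the protocol.

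- Section 1.8 (overview): "children will complete the questionnaire separately too on days 0,1,3, 7, 14 21 and 28". The sentence is garbled. The list may apply to all completion, or only to the older child's own questionnaire.
- Section 5.12, Quality of life: "The questionnaire will be completed by parents/carers proxy for all patients at days 0,1,7,14,21 and 28". The same paragraph restricts children under 4 to the VAS.
- Section 8 (health economics): the instrument "will be used in conjunction with the clinical outcome measures at days (1,7,14,21,28"). PedsQL is named in the same sentence, so the list may cover both instruments.

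The QALY method is the same in both economic sections. Section 5.14 says "Accumulated costs and QALYs will be calculated through area under the curve methods for each patients", and section 8 says "Accumulated costs and QALYs for each individual will be calculated based on an" area-under-the-curve approach. Section 5.14 also adjusts for baseline difference.

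Section 5.12, Severity of symptoms, explains a secondary outcome measured early in the illness. It opens with "The rationale for choosing the severity in the first 2-4 days after seeing the doctor" and gives as its reason that "this is the time when symptoms are the most severe". It adds that antibiotics might make a difference then.

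**The concern.** The three lists cannot all be followed. Two of them, including the one in the economic plan, leave days 2 to 6 without a quality-of-life measurement, and section 8 also omits day 0.

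An area under the curve knows nothing between two measurement points except the straight line that joins them. If the treatment difference in utility is largest on days 2 to 4 and has faded by day 7, the line from day 1 to day 7 passes beneath it. The same holds for an early harm, such as diarrhoea or nausea during the course.

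Assessment days are a matter of data collection. A day-3 questionnaire that was never completed cannot be recovered by a later analysis plan. What is at stake is the incremental cost per QALY, one of the two cost-effectiveness measures named in sections 5.14 and 8.

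**Working it through.** The protocol gives no QALY figure to reproduce. The check takes the three day lists as inputs and applies the trapezoid rule, that is, linear interpolation between measurements.

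**Step 1. Weights.** Each interior day carries (gap before)/2 + (gap after)/2. Each end day carries half of its one gap.

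| Schedule | Day 0 | Day 1 | Day 3 | Day 7 | Day 14 | Day 21 | Day 28 | Total (days) |
|---|---|---|---|---|---|---|---|---|
| Section 1.8 | 0.5 | 1.5 | 3.0 | 5.5 | 7.0 | 7.0 | 3.5 | 28 |
| Section 5.12 | 0.5 | 3.5 | none | 6.5 | 7.0 | 7.0 | 3.5 | 28 |
| Section 8 | none | 3.0 | none | 6.5 | 7.0 | 7.0 | 3.5 | 27 |

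Where day 3 is measured, its weight is (3 − 1)/2 + (7 − 3)/2 = 3 days, or 3/7 = 43% of the first week. Read literally, the section 8 list covers 27 days and not 28.

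**Step 2. What day 3 adds.** Let D1, D3 and D7 be the differences between arms in utility on days 1, 3 and 7. Subtracting the section 5.12 weights from the section 1.8 weights gives

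(1.5 − 3.5)·D1 + 3·D3 + (5.5 − 6.5)·D7 = 3·D3 − 2·D1 − D7.

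With no difference on day 1 and a difference d on day 3, this is 3d − D7. It is largest, at 3d, when the arms are also equal on day 7, and it shrinks as the difference persists.

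**Step 3. Share of the true effect captured.** The protocol gives no utility curve, so these shapes are assumptions. In each, the difference is zero up to day 1, reaches d on day 2 and changes linearly between the stated days.

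| Assumed shape | True area | With day 3 | Without day 3 |
|---|---|---|---|
| Full on days 2 to 4, zero by day 5 | 3.0d | 3.0d (100%) | 0 (0%) |
| Full on days 2 to 6, zero by day 7 | 5.0d | 3.0d (60%) | 0 (0%) |
| Full on days 2 to 4, 20% left on day 7, zero by day 14 | 5.0d | 4.1d (82%) | 1.3d (26%) |
| Full on days 2 to 4, 50% left on day 7, zero by day 14 | 6.5d | 5.75d (88%) | 3.25d (50%) |
| Full on days 2 to 7, zero by day 10 | 7.0d | 8.5d (121%) | 6.5d (93%) |

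Third row as an example: with day 3, 3·d + 5.5·0.2d = 4.1d; without it, 6.5·0.2d = 1.3d. The lists in sections 5.12 and 8 give the same results here because the difference is zero on days 0 and 1.

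**Step 4. Size.** For a difference confined to days 2 to 4 the amount missed is 3d. With d assumed between 0.05 and 0.20:

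- 3 × 0.05 = 0.15 utility-days, and 0.15/365.25 ≈ 0.0004 QALY;
- 3 × 0.20 = 0.60 utility-days, and 0.60/365.25 ≈ 0.0016 QALY.

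**The case against.** The strongest reply is that little more than an editing slip has been shown, and parts of that reply stand.

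- **Section 1.8 may not set the proxy schedule.** Its day list can be read as belonging to the child's own completion, while section 5.12 gives the proxy schedule for every patient. On that reading, adding day 3 to the proxy is an improvement to the design as well as a reconciliation. This stands, and it also means that the proxy QALY has no day-3 value.
- **Appendix D, Table 1 may hold the operative schedule.** Its content did not survive in the text available for this review. If it gives a single schedule, that settles what sites do, but the three prose lists still need correcting.
- **The QALY is not the only economic measure.** Cost per symptomatic day prevented draws on the daily diary, which covers days 2 to 6, and side effects are recorded daily too. This stands and limits the consequence to the QALY.
- **The amount is small, and d is assumed.** Both are true. A utility difference also does not carry over directly to children under 4, who provide only the VAS. Whether 0.0004 to 0.0016 QALY matters to a decision depends on an incremental cost that the protocol does not give.

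Two stronger readings are tempting. One is that the QALY is blind to the only period in which benefit is expected. Section 5.12 does not call days 2 to 4 the only such period, and the primary outcome follows symptom duration for up to 28 days. A benefit that lasts to day 7 is captured to the extent of 26% to 93% in the assumed cases. In the last case in the working, the schedule without day 3 is the closer of the two, because the long gap from day 7 to day 14 makes the other overshoot.

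The other is that section 8 would adjust for a baseline taken after dosing. Section 5.12 states day 0, and section 8 may list follow-up points only. Section 6.3 counts doses from day 1 but does not say whether the day-1 questionnaire precedes the first dose.

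**Conclusion.** The protocol contradicts itself on when the EQ-5D-Y is completed, and this holds on its face. Under the lists in sections 5.12 and 8, the area-under-the-curve QALY can understate a benefit or harm concentrated on days 2 to 4. The understatement is total only if the arms are equal on both day 1 and day 7, and partial if a difference remains on day 7.

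For an effect confined to days 2 to 4, the most that can be missed is about 0.0004 to 0.0016 QALY per child, given an assumed utility difference of 0.05 to 0.20. That range rests on linear interpolation and on assumed curves, since the protocol supplies none.

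The point concerns a secondary economic measure and leaves the primary outcome untouched. It should be corrected because the missing value cannot be recovered at analysis and the correction is cheap.

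**What to change.** State one EQ-5D-Y schedule in sections 1.8, 5.12 and 8 and in the diary: days 0, 1, 3, 7, 14, 21 and 28 for the parent proxy, with VAS only for children under 4. Check Appendix D, Table 1 against it. Reword the section 1.8 sentence so that it is clear which days apply to the proxy and which to the older child's own questionnaire. In section 8, say whether PedsQL follows the same days. Name day 0 as the baseline for the adjustment in section 5.14.

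The cost is wording in these sections and one extra short questionnaire page in week 1, when parents already complete a daily diary. The downside is a slightly heavier first week for families.

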#### Return with new or worsening symptoms or complications

These outcomes will be documented based on a structured notes review, which we have shown to be feasible. This outcome was one of the more useful outcomes to demonstrate antibiotic effectiveness in a previous large trial in adults. (10)

### 5.13. Health care resource use

Information on resource usage will be collected for all participants through notes review at the end of the study (28 days) covering medication, primary care visit community services, A&E attendance, out-patient appointment together with a Case Report Form (CRF) in which detailed resource use on hospital will be collected. The CRF will include resource use for major adverse events (e.g. anaphylaxis, complications, hospital admission). This will be used to assess any use of NHS and social services (primary care visits, community services, hospital inpatient and outpatient visits and A&E attendances.) In addition parent/carer's time off work in taking care of children will be collected through parents' diary.

### 5.14. Cost-effectiveness

The economic analyses will be taken from the NHS and PSS perspective. All resource usage will be priced based on published information (BNF, National reference costs and PSSRU). Accumulated costs and QALYs will be calculated through area under the curve methods for each patients. Missing value will be imputed using multiple imputation approach. Generalised linear model will be used to estimates the differences in costs and QALYs between the study groups and adjusted baseline

difference. If the intervention is proved to be effective, incremental costs per symptomatic day prevented and cost per quality adjusted life year gained will be estimated. Cost effectiveness acceptability curves will also be produced to illustrate the uncertainty.

## 5.15. Sample size calculation

Pilot phase: there is no sample size calculation.

Main phase: An alpha of 0.01 is chosen to allow for 5 pre-specified subgroups, which occur in at least 30% of children based on our previous data (sputum (65%), fever (64%); generally unwell rated as a bad problem (30%); short of breath (36%) abnormal chest signs (crepitations: 43% ). Previous consensus documented less than 2-3 days difference in symptoms rated moderately bad or worse is unlikely to be a sufficient reason to prescribe antibiotics, and 3 days should probably now be the minimum given the short and long term disadvantages of antibiotics, (9, 10) and in particular increased national and international concern over the danger of antibiotic resistance (<https://www.gov.uk/government/publications/resources-to-support-the-2012-european-antibiotic-awareness-day-in-england>; <https://www.gov.uk/government/news/prime-minister-warns-of-global-threat-of-antibiotic-resistance> ). (3, 4) To detect a hazard ratio for the treatment interaction of 1.7 (see Appendix 2 to this protocol: equivalent to 3 days difference between a subgroup and the whole sample), for the smallest subgroup of interest (30% of the sample), using the equations of Schmoor et al requires 738 individuals for 80% power and 938 individuals for 90% power (assuming 80% follow-up). (36) The other (larger subgroups) will have greater power. To allow for some leeway in our assumptions we will aim to recruit at least 1000 children.

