## 1.9. Sample size

938 children are required (for alpha=0.01, 90% power, 80% follow-up) to detect a 3 day difference in the effect of antibiotics for the primary outcome among any one of 5 clinical subgroups (see below). We assume a subgroup represents at least 30% of the sample (our data suggests 30-65% for each of the key subgroups).

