### 9.3. The Level of Statistical Significance

A 5% significance level will be used for testing effects in the whole cohort and a 1% significance level for the testing of subgroup interactions, as per the sample size calculation.

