## 18. APPENDIX B. POWER FOR INTERACTIONS FOR THE SMALLEST CLINICAL SUBGROUP

(assuming 30% of the sample in the subgroup, for alpha=0.01 and assuming 80% follow-up); the proposed effect size is in bold

	80% power						
Interaction effect (days)		2	3	3.5	3.75		
Interaction Hazard ratio (HR)		1.4	1.7	1.9	2.0		
Total sample size		1808	738	509	442		
	90% power						
Interaction effect (days)		2	3	3.5	3.75		
Interaction HR		1.4	1.7	1.9	2.0		
Total sample size		2304	938	650	558		

[figure not shown]

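### Section 5.15 describes its interaction as subgroup versus whole sample, when it is subgroup versus remaining children, and equates it with the 3-day prescribing threshold without stating that this assumes no benefit in those children

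*Protocol*

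**What the plan says.** Section 5.15 of the protocol starts from a clinical threshold: "less than 2-3 days difference in symptoms rated moderately bad or worse is unlikely to be a sufficient reason to prescribe antibiotics". It then argues that 3 days should now be the minimum. The sample size follows: "To detect a hazard ratio for the treatment interaction of 1.7", described as "equivalent to 3 days difference between a subgroup and the whole sample", for the smallest subgroup (30% of the sample), "requires 738 individuals for 80% power and 938 individuals for 90% power (assuming 80% follow-up"). The recruitment aim is then rounded up to at least 1000.

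Section 1.9 words the target as "to detect a 3 day difference in the effect of antibiotics for the primary outcome among any one of 5 clinical subgroups". Appendix B places the same 3 days in a row for the interaction effect in days, "assuming 30% of the sample in the subgroup, for alpha=0.01 and assuming 80% follow-up". Its 2-day column (hazard ratio 1.4) needs 1808 children for 80% power and 2304 for 90%.

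Section 9.3 sets the levels: "A 5% significance level will be used for testing effects in the whole cohort and a 1% significance level for the testing of subgroup interactions". Sections 1.11 and 9.1 also plan estimates of effect within each key subgroup.

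**The concern.** Two things are run together.

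First, the comparator. An interaction term for a yes/no subgroup in a Cox model is the ratio of the treatment effect in the subgroup to that in its complement. The whole sample contains the subgroup, so a contrast with it is a smaller quantity, and the shrinkage differs from subgroup to subgroup.

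Second, the meaning of 3 days. The consensus in 5.15 concerns how much benefit justifies prescribing, which is antibiotic versus none in the child concerned. The power calculation applies those 3 days to a difference between two treatment effects. The two coincide only if the effect outside the subgroup is zero. The protocol does not state that premise, and section 3 allows for moderate benefit both overall and among subgroups.

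At stake is how a non-significant interaction is read. The stated sensitivity is 3 days with 90% power. A subgroup that gains 3 days while other children gain 1 meets the protocol's prescribing threshold, yet is only about a 2-day interaction, for which the trial has far less power.

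**Working it through.** **Inputs.** Alpha 0.01, hazard ratio 1.7, 30% subgroup, 80% follow-up, N = 938 for 90% and 738 for 80% power (5.15, Appendix B); 2 days = hazard ratio 1.4 (Appendix B). Assumed here: 1:1 allocation, two-sided alpha, and every followed child reaching the event by day 28.

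**1. Comparator.** Let e1 be the benefit in the subgroup, e0 the benefit elsewhere and q the subgroup's share.

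- Whole-sample effect = q·e1 + (1 − q)·e0, so e1 − whole = (1 − q)·(e1 − e0).
- q = 0.30, 3 days against the remaining children: 0.70 × 3 = 2.1 days against the whole sample.
- q = 0.30, 3 days against the whole sample: 3 / 0.70 = 4.3 days against the remaining children.
- q = 0.65 (sputum): 0.35 × 3 = 1.05 days against the whole sample.

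The gloss in 5.15 therefore means something different for each subgroup.

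**2. The plan's own figure.** Standard interaction formula: events = (z_alpha + z_power)² / [0.25 · q(1 − q) · (ln HR)²], N = events / 0.8.

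- 90% power: (2.576 + 1.282)² / [0.25 × 0.21 × 0.5306²] = about 1007 events, N = about 1259, against 938 stated.
- 80% power: about 790 events, N = about 988, against 738 stated.

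The stated totals are not reproduced. They lie within 2% of a two-arm Freedman calculation inside the 30% subgroup:

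- 90% power: 222 events / (0.3 × 0.8) = 925.
- 80% power: 174 events / (0.3 × 0.8) = 725.

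That is a separate matter, but it means power has to be shown in two ways.

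**3. Power when the other children gain 1 day.** The subgroup gains 3 days, so the interaction is 3 − 1 = 2 days, hazard ratio 1.4 in Appendix B.

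- *Stated 90% at face value.* Non-centrality at 1.7 is 2.576 + 1.282 = 3.857. At 1.4 it is 3.857 × ln 1.4 / ln 1.7 = 3.857 × 0.3365 / 0.5306 = 2.446. Power = Φ(2.446 − 2.576) = 45%.
- *Standard formula at N = 938.* Events 938 × 0.8 = 750; √(750 × 0.25 × 0.21) = 6.28. At 1.7: Φ(6.28 × 0.5306 − 2.576) = 77%. At 1.4: Φ(6.28 × 0.3365 − 2.576) = 32%.
- *Sensitivity to the conversion of days.* Appendix B's pairs fit HR = T/(T − d) with T of about 7.0 to 7.5 days. A 1-day gain elsewhere is then a hazard ratio of 1.167 to 1.154, so the interaction is 1.7/1.167 = 1.46 to 1.7/1.154 = 1.47. The standard formula gives 42% to 44%. If the others gain 2 days, it gives 9% to 12%.

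**4. Within-subgroup comparison.** Events 750 × 0.3 = 225; √(225 × 0.25) = 7.50. Power for hazard ratio 1.7 at alpha 0.01 = Φ(7.50 × 0.5306 − 2.576) = 92%. This does not depend on what happens in the other children.

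**The case against.** A reader might infer that subgroups with a worthwhile benefit will be missed by the trial. The documents do not support that. Sections 1.11 and 9.1 plan estimates overall and within the key subgroups, section 4 makes effectiveness in those subgroups an objective, and the within-subgroup comparison has about 92% power at 1% for 3 days in the smallest subgroup. If the other children gain 1 day, the 5% whole-cohort test also has about 95% power (same T conversion), although it would not single out the subgroup. Nor does any section say that a null interaction rules out benefit. That reading is a risk, made easier by the lay summary's claim that the study is large enough to show which groups benefit and which do not.

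It can also be said that powering for heterogeneity is deliberate (section 3), that little effect outside the subgroup is a plausible premise given the adult evidence in section 2, and that Appendix B openly shows the larger numbers for a 2-day interaction. All of this stands. With zero effect elsewhere the mismatch in meaning disappears. It remains that the premise is unstated and that the comparator in 5.15 is wrong whatever the premise.

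Finally, how subgroup results are interpreted may be left to an analysis plan. That does not answer a contrast which the protocol itself states wrongly.

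**Conclusion.** The point holds as a misdescribed effect size and an unstated assumption, not as a defect in the planned estimates. The error in the comparator is exact arithmetic: for a 30% subgroup, 2.1 days against 3, or 3 against 4.3, depending on which reading of 5.15 is taken.

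The loss of interaction power when other children gain 1 day depends on assumptions: about 45% if the stated 90% is accepted, about 32% by the standard interaction formula at hazard ratio 1.4, and 42% to 44% by that formula if days are converted on a ratio scale. All are well below 90%. The figures rest on 1:1 allocation, two-sided alpha, all followed children reaching the event, and N = 938. At the recruitment aim of 1000, the standard formula gives 81% for hazard ratio 1.7 and 35% for 1.4 (800 events, √(800 × 0.25 × 0.21) = 6.48).

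The consequence is confined to what a non-significant interaction can be said to show.

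**What to change.** - **Section 5.15:** name the remaining children as the comparator in place of the whole sample. State that equating 3 days with the prescribing threshold assumes no benefit in those children, and that power is much lower if they also benefit. Recompute that power with the interaction formula. Do not print 45%, which relies on 938 giving 90% interaction power.
- **Section 1.9:** its wording differs from 5.15 and can be read either way, so state there that the 3-day difference is an interaction, subgroup against remaining children.
- **Interpretation:** state that the 3-day threshold is judged on the already planned amoxicillin-placebo estimate within each subgroup and its confidence interval. The interaction test then serves as evidence of heterogeneity, and a null interaction is not read as excluding a 3-day benefit.

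The cost is wording, with no more patients and no change to the planned estimates. The downside is that the stated sensitivity becomes less favourable.

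### The 738/938 sample sizes do not give the stated 80%/90% power for an interaction hazard ratio of 1.7 with 80% follow-up; 938 gives about 78% and the target of 1000 about 81%

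*Protocol*

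**What the plan says.** Protocol section 5.15 sets the design target: "To detect a hazard ratio for the treatment interaction of 1.7", described as "equivalent to 3 days difference between a subgroup and the whole sample", "for the smallest subgroup of interest (30% of the sample"). It concludes that this "requires 738 individuals for 80% power and 938 individuals for 90% power (assuming 80% follow-up"). The significance level is explained by multiplicity: "An alpha of 0.01 is chosen to allow for 5 pre-specified subgroups".

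Section 1.9 gives the same total as the recruitment requirement: "938 children are required (for alpha=0.01, 90% power, 80% follow-up) to detect a 3 day difference". Appendix B tabulates totals for interaction HRs of 1.4, 1.7, 1.9 and 2.0 under the same conditions: "assuming 30% of the sample in the subgroup, for alpha=0.01 and assuming 80% follow-up".

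Section 5.15 then rounds the recruitment aim up to at least 1000, as leeway in the assumptions. Section 9.3 ties the analysis to this calculation by setting "a 1% significance level for the testing of subgroup interactions, as per the sample size calculation".

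**The concern.** All three places say that 80% follow-up is already allowed for, so 938 should be the number of children to recruit for 90% power. An interaction test at alpha 0.01 with only 30% of children in the subgroup is demanding, and 938 looks too small for it.

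The interaction is what the trial is built on. Section 3 argues that a trial powered only for the average effect would not persuade prescribers, and the lay summary promises that the study is large enough to show which groups benefit and which do not. If the stated power is too high, a null interaction will be read as stronger evidence against differential benefit than it is.

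**Working it through.** **Inputs from the protocol.** Interaction HR 1.7, subgroup prevalence p = 0.30, alpha 0.01 and 80% follow-up (5.15, Appendix B). The primary analysis is complete case (9.4, 9.5), so children lost to follow-up contribute no events.

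**Assumptions.**
- Two-sided test. The protocol does not state this, but 938/738 = 1.271 fits two-sided 0.01 (14.88/11.68 = 1.274) better than one-sided 0.01 (1.297).
- 1:1 allocation. This is not stated for the main phase; the pilot target has equal groups.
- Every followed child reaches the endpoint by day 28. This is the most favourable case.

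**Formula.** For a treatment-by-subgroup interaction in a Cox model, events D = (z₀.₉₉₅ + z_power)² × 4 / [p(1 − p)] / (ln HR)², and recruited N = D / 0.8.

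- 4 / (0.30 × 0.70) = 19.05
- (ln 1.7)² = 0.5306² = 0.2816
- 80% power: (2.576 + 0.842)² = 11.68, so D = 11.68 × 19.05 / 0.2816 = 790 and N = 988
- 90% power: (2.576 + 1.282)² = 14.88, so D = 14.88 × 19.05 / 0.2816 = 1007 and N = 1259 (rounded up)

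The printed 738 and 938 are about 25% below these recruitment totals. They are also below the event counts before any allowance for loss.

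**Power delivered.** Power = Φ(√(0.8N / 19.05) × ln HR − 2.576).

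| Recruited | HR 1.70 | HR 1.7325 | HR 1.7499 |
|---|---|---|---|
| 738 (stated 80%) | 64.7% | 68.6% | 70.5% |
| 938 (stated 90%) | 77.5% | 80.9% | 82.5% |
| 1000 (target) | 80.6% | 83.8% | 85.3% |

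For 938 at HR 1.70: 0.8 × 938 = 750 events; √(750 / 19.05) = 6.28; 6.28 × 0.5306 − 2.576 = 0.755; Φ = 0.775.

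**Could rounding of the HR explain it?** The largest HR that prints as 1.7 (1.7499) still needs about 905 events, or 1132 recruited, for 90% power.

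**Could prevalence explain it?** At HR 1.7 and 938 recruited, power is 82% at 36% prevalence, 85% at 43%, 82% at 64% and 81% at 65%. The maximum, at 50% prevalence, is 85.5%.

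**Where might 738/938 come from?** Two calculations come close across Appendix B (80%/90% power):

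| HR printed | Appendix B | Interaction, no allowance for loss | HR implied by Appendix B, no allowance | Effect inside the 30% subgroup only (Freedman), divided by 0.8 |
|---|---|---|---|---|
| 1.4 | 1808/2304 | 1965/2503 | 1.42 | 1752/2232 |
| 1.7 | 738/938 | 790/1007 | 1.73 | 724/922 |
| 1.9 | 509/650 | 540/688 | 1.94 | 505/644 |
| 2.0 | 442/558 | 463/590 | 2.03–2.04 | 438/558 |

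The third column is 5% to 9% above the printed totals, but the HRs implied without inflation all round to the printed ones. With inflation, the implied HRs are 1.48, 1.85, 2.09 and 2.21–2.22, and none rounds to its label. The last column includes the follow-up allowance and lies within about 3% of every cell, but it is not an interaction test.

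**The case against.** A reader might infer that the authors simply forgot to divide by 0.8. The documents do not establish that. No working is shown, and at the printed HRs the un-inflated interaction formula misses every cell. The within-subgroup calculation fits the printed HRs more closely and does include follow-up; on that reading the error is one of labelling. This objection to naming a cause stands. It does not rescue the stated power, because interaction power at a given N is the same however N was obtained.

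It is also fair to say that 78% is the low end. If the unrounded HR was about 1.73, then 938 gives about 81%. The actual plan is to recruit at least 1000, and the 30% subgroup is the worst of the five: at 1000 and HR 1.7, the subgroups at 36% to 65% prevalence have about 84% to 87%. All of this stands, and all of it is still below 90%.

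A third argument takes the comparison with the whole sample literally. If 1.7 were the ratio of the subgroup effect to the overall effect, the ratio to the remaining children would be about 1.7^(1/0.7) = 2.13, and 938 would give about 98.5% power. That reading conflicts with the protocol's own term, a hazard ratio for the treatment interaction, and does not reproduce 938. It does show why the comparator must be stated correctly.

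**Conclusion.** The power statement is wrong as written. For an interaction HR of 1.7 in a 30% subgroup, 938 recruited gives about 78% power (at most 82.5% for any HR that rounds to 1.7), and the target of 1000 gives about 81% (at most about 85%). The false-negative risk at 938 is therefore about 18% to 22%, and at 1000 about 15% to 19%, against a stated 10%. HRs detectable with 90% power are about 1.85 at 938 and 1.81 at 1000.

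This rests on a two-sided test, 1:1 allocation and an event in every followed child; any child still unresolved at day 28 would lower the power further. The cause of the discrepancy remains open.

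A reader might also infer that the trial must recruit 1259, or that the design fails. The documents do not support that: 1000 recruited still gives about 80% power for the smallest subgroup, and the whole-cohort test at 5% is a separate test that this calculation does not affect.

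**What to change.** Correct sections 1.9, 5.15 and Appendix B together:

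- Show the formula, the sidedness, the allocation ratio, the unrounded HR and the follow-up step.
- Keep the aim of at least 1000 and state what it delivers: about 81% power for an interaction HR of 1.7 in a 30% subgroup, or 90% power for an HR of about 1.81.
- Replace the Appendix B totals. At the printed HRs of 1.4, 1.7, 1.9 and 2.0 and 80% follow-up, the formula gives, rounded up, 2457, 988, 675 and 579 for 80% power and 3130, 1259, 860 and 738 for 90% power. If unrounded HRs were intended, print those and recompute.
- Say that the interaction HR compares the subgroup with the rest of the sample, and check the 3-day equivalence against that definition.

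The cost is a wording and table correction and a less favourable stated power. No extra patients are needed.
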